The proposed trial is *highly innovative* and represents a paradigm shift in current treatment strategies for the prevention and treatment of DSP for patients with and without diabetes. We strongly contend that the diabetes research community must move beyond glucose control alone to more comprehensive treatment approaches for diabetic complications. Moreover, a successful trial would bring us one step closer to a desperately needed intervention for patients without diabetes, including the large obese population, to prevent and improve DSP. The *innovation* in this proposal is high and includes: 1) an exercise regimen (HIIT) that is time efficient, yields improved metabolic health even after short term participation, and is better tolerated with higher compliance in an obese population than conventional exercise; 2) a study design that allows comparisons between exercise, bariatric surgery, and the combination of these interventions without the need for an expensive, randomized surgical intervention phase 2 trial; 3) a main outcome measure (IENFD), which allows sensitive and objective

quantification of nerve fiber loss and regeneration over time, with true potential to capture early changes of DSP; 4) comprehensive patient-oriented outcomes, including multiple measures of DSP-related pain, daily function, and DSP-specific quality of life outcomes; 5) the use of a non-invasive measure of DSP, corneal confocal microscopy (CCM), to compare with the primary outcome of this trial, IENFD, to inform future clinical trials (see C.3.4.2); and 6) an analysis plan that investigates the potential modifying effects of sex on DSP outcomes, the differential effect of sleeve gastrectomy versus Rou-en-Y gastric bypass on DSP outcomes, and the weight loss independent effects of bariatric surgery by incorporating early outcome measures.

C. Approach

The clinical trial design summary for Aims 1 and 2 is shown in Figure 1. All patients will be recruited from a **Bariatric Surgery** Clinic, including those that do and those that do not have surgery. We will randomize patients 1:1 to either the HIIT exercise regimen or routine exercise counseling. Randomization will be stratified 1:1 for

those that do and

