In addition to the above exercise studies on DSP outcomes, our current NIH K23 study is following 130 obese participants for 2 yr following a diet-induced weight loss intervention with limited exercise counseling. ¹⁷ Our preliminary data reveal that IENFD increased by only 0.2 fibers/mm at both the distal leg and proximal thigh despite an average improvement in BMI of 3.67 kg/m². This is in contrast to the two previously mentioned exercise trials demonstrating IENFD improvements of 1.4 and 1.68 fibers/mm after 1 yr and 10wk respectively. ³⁰ Taken together, these studies support our hypothesis that exercise is the most likely intervention to improve DSP outcomes. Given the natural history of IENFD decline over time, diet-induced weight loss is also likely to improve DSP outcomes, but not to the same degree as exercise. Importantly, the effect of surgical weight loss on IENFD is unknown.

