C2.2.1 Justification for bariatric surgery: Similar to the ideal exercise regimen, the best weight loss strategy would improve metabolic outcomes and have high compliance. Just like HIIT, bariatric surgery meets those criteria. Mounting evidence supports bariatric surgery for improvements in metabolic syndrome components including diabetes, hypertension, and dyslipidemia. In terms of diabetes, a prospective, longitudinal study of 28,616 obese diabetic patients undergoing a variety of surgical approaches revealed remission or improvement of diabetes in 44-83% of participants.⁵² These results have been duplicated in four randomized controlled trials of surgery compared with medical management or lifestyle interventions. 53-56 Most of these trials looked at diabetes outcomes at 1-2 yr, but data at 3-5 yr is also promising. 57, 58 All four trials revealed large effect sizes regardless of the type of surgery employed. Data to support a reduction in hypertension are less robust compared with diabetes. A large prospective, longitudinal study found resolution or remission of hypertension ranging from 44-79% depending on the surgical procedure.⁵² However, a randomized trial of surgery compared with lifestyle and medical modifications demonstrated similar large reductions in systolic blood pressure at 1 year. 54 Whether the difference in long term compliance in these groups would result in different long term hypertension outcomes is unclear. Data on dyslipidemia are similar to that for hypertension. The same large prospective, longitudinal study found remission of dyslipidemia ranging from 33-66% at 1 year depending on the surgical procedure performed. 52 No randomized data demonstrating a reduction in dyslipidemia are available to provide higher levels of evidence. In terms of reducing obesity, bariatric surgery is incredibly effective and the effect is long lasting. Patients lose between 45-85% of their excess weight, with maximum weight loss between 1-2 yr after the procedure. 59, 60 In addition, surgery results in longstanding weight loss that is sustained up to 10 yr after the procedure. 26 Medical weight loss with dietary or pharmacologic interventions is often successful in the short term, but in contrast to surgery, it is difficult to sustain. The lack of concern regarding compliance is one of the main reasons why studying a bariatric surgery population is preferred to studying a medical weight loss population. In addition to the data supporting the effect of bariatric surgery on improving metabolic outcomes and the inherently high compliance, one small study supports a possible effect on DSP outcomes. Specifically, a prospective cohort study of 20 patients with type 2 diabetes undergoing a Roux-en-Y gastric bypass revealed that the 12 patients with pre-operative DSP had significant improvements in DSP outcomes measures 6 mo after surgery. Of note, no control group was provided and outcome measures were not masked to the intervention. Despite these limitations in study design, these results are encouraging for a possible positive effect on DSP outcomes after bariatric surgery.⁵¹

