C3.2.1 HIIT: Training sessions during the 24-mo will be supervised by exercise physiologists and trainers. [name], the director of the Human Phenotyping Core (HPC) of the U-M's Nutrition and Obesity Research Center will provide oversight of this aspect of the study given his vast expertise on the impact of HIIT and other exercise interventions on metabolic outcomes.⁴⁶⁻⁵⁰ The exercise modality will be self-selected (e.g., walk/run (outdoors or treadmill), elliptical machine, stair climbing, cycling), and subjects will be encouraged to regularly vary the exercise modality to reduce risk of overuse injury and to enhance the variety of the exercise program.

Subjects receiving the surgery intervention will start the HIIT regimen no sooner than 4 wk post-operatively to provide an adequate time to heal from the procedure. All subjects will first undergo a familiarization program for 1 week where they all will perform conventional exercise (steady-state at 65% HR max for 25 min/session). After this 1-week familiarization period, subjects will begin the HIIT regimen. The first session of the "ramp-up" period will entail 19 min of conventional exercise at 65% HR max, followed immediately by 2 x 1 min intervals at 90% HR max with a 1 min active recovery period between intervals at 50% HR max, and a 3 min cool down at 60% HR max after the second interval. After that first ramp up training session, 1 additional high intensity interval will be added to each training session, so by the beginning of week 3 of HIIT training, subjects will reach the full HIIT training protocol of a total of 10 x 1 min intervals at 90% HR max (**Figure 2**). They will continue this training protocol, 3 sessions/wk (2 supervised and 1 unsupervised), for 24-mo. Subjects who may feel challenged by the rate of increase in the number of intervals during this ramp up period will be allowed to increase the number of intervals at a slower pace, but all subjects must reach the full HIIT protocol during week 4 of HIIT training. Of note, our team regularly has patients with obesity and/or diabetes progress to the full protocol HIIT within 3 weeks, demonstrating the feasibility of this training approach in our population. 38, 41, 62, 63

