- C3.2.3 Bariatric surgery: Patients will undergo the surgical procedure as recommended by their surgeon as part of their routine care at a bariatric clinic. Our preliminary data indicates that 85% of patients had a sleeve gastrectomy, 15% had a Rou-en-Y gastric bypass at the University of Michigan, and none had an adjustable gastric band. We expect a similar distribution of procedures as part of this proposed study. Patients undergoing sleeve gastrectomy and Roux-en-Y gastric bypass have similar weight loss and time to stabilization, which limits potential confounding by type of surgical procedure. ^{59, 60} Specifically, weight loss is typically 60-80 pounds at 6 mo, and 100-120 pounds at one year with stabilization at 1-1.5 yr. In contrast, adjustable gastric band procedures result in a 45-55 pound weight loss at 6 mo with stabilization at 2 yr, but this procedure is not performed at U-M. Of note, as part of their routine post-operative care, patients are supplemented with a multivitamin, sublingual B12, and calcium. Furthermore, patients have laboratory monitoring including comprehensive metabolic panel, complete blood count, B12, TSH, ferritin, and vitamin D. The prophylactic supplementation and laboratory monitoring mitigate the potential for nutritional deficiencies to lead to nerve injury and subsequent DSP. The strength of this approach is that it mirrors current practice in the bariatric surgery, a specific nutritional deficiency other than B12 deficiency is often not found. ⁶⁸
- **C3.3. Metabolic phenotyping:** These tests will aid in the appropriate description of the population, allow for adjustment of potential confounding as needed, and may provide further data in support of the metabolic factors that improve when IENFD increases over time.

Phenotypic tests will occur at baseline, 3, 12, and 24 mo, with the exception of the GTT which will only be performed at baseline. The metabolic phenotyping tests include:

 2 hr, 75 gram oral GTT with glucose and insulin levels drawn at 0, 30, 60, 90, and 120 min to allow categorization of glycemic status as well as calculation of Oral Glucose Insulin Sensitivity (OGIS).
Participants with a known diagnosis of diabetes will not complete an OGTT. Participants with a fasting glucose >126 mg/dL will not complete the test. Fasting glucose and insulin levels will be drawn at the 3, 12 and 24 month time points;

- 2. Hemoglobin A1C;

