- 14. Aerobic Assessment: All participants enrolled in the study will participate in brief graded exercise test (bike or treadmill) to determine maximal aerobic capacity (VO₂max). Participants randomized to the HIIT cohort will also complete a second VO₂max test after the training intervention to document the change in aerobic fitness. This exercise test is routinely used in clinical research projects to assess aerobic fitness in lean, obese and other clinical populations.
- 15. Dual Energy X-ray Absorptiometry: Body composition will be measured, including body fat, muscle mass and bone density using low-dose x-ray. All participants enrolled in the study will complete a DEXA scan at the beginning and end of the study.
- 16. BodPod: Subjects that exceed the weight limits of the dual energy x-ray absorptiometry may complete the BodPod as an alternative in order to determine body composition. Subjects will complete at baseline and at the end of the study.

C3.5. Visits schedule (Table 6):

| Table | 6: Study Events Sc | | | | |
|---|--------------------|--------------|------------|----------|----------------|
| Visit Number | er Visit 1 | Visit 2 | Visit 3 | Visit 4 | Visit 5 |
| Visit Descriptio | n Screening | Baseline | Outcomes | Outcomes | Outcomes |
| Time poir | nt Before baseline | Day -70 to 0 | Month 3 | Month 12 | Month 24 |
| Visit windo | w NA | 70 days | ± 14 d | ± 14 d | ± 14 d |
| Informed Consent^/study criteria | | | | | |
| Medical History Review | X | | | | |
| Stress Test | X | | | | |
| Randomized to Exercise Protocol | | X* X | | | |
| Laboratory Measures | | X | X | X | X |
| Biorepository Measures | | | | | |
| Plasma | | X | X | X | X |
| Urine | | X | | | X |
| Subcutaneous Adipose Tissue | | X | | | X |
| DNA | | X | | | |
| Skin Biopsies (IENFD) ^T | | Х | Χ | Х | X |
| Corneal confocal microscopy | | Х | Х | Х | Х |
| FDT-24-2 | | X | X | X | X |
| Retinal Imaging | | X | Χ | X | X |
| Electrophysiologic measures | | Х | | | |
| NCS | | X | | | X |
| Cardiovascular reflex tests | | | | | X |
| Cardiovascular reliex tests | | | | | |
| Clinical measures | | | | | |
| Neurologic examination | | X | | | X |
| MNSI, UENS, mTNS, SAS, DNS, DN4 | | X | X | X | X |
| McGill pain questionnaire, NRS | | Х | X | Х | Х |
| Qualitative sensory testing | | | | | |
| Neurotheisiometer | | X | X | X | X |
| | | | | | |
| Cognitive impairment | | | | | |
| NIH Toolbox | | X | | | X |
| Rey | | X | | , , | X |

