
C3.7.2 Analyses of secondary outcomes: Due to the pitfalls of multiple testing, formal statistical testing won't be performed. For analysis of repeated measures of continuous data (CCM, cardiovascular reflex tests, MNSI, UENS, mTNS, SAS, McGill Pain questionnaire, NeuroQOL, and functional assessments), the longitudinal approaches described above will be employed. Specifically, each outcome will be analyzed separately using a linear mixed effect regression model, with the treatment group as the primary exposure.

C3.7.3 Exploratory analyses: To investigate the potential modifying effects of sex, we will perform an additional analysis that includes an interaction term between the intervention groups and sex. Similarly, we will explore the differential effect of sleeve gastrectomy versus Rou-en-Y gastric bypass by including separate indicator variables for these two different surgical techniques. We will also investigate the potential weight loss independent effects of bariatric surgery by evaluating the earliest time point (3 months). In addition to other metabolic syndrome components, we will study the effect of change in insulin sensitivity as measured by OGIS on our primary outcome. Finally, we will perform an analysis of those who complete more than 80% of supervised exercise sessions to assess the effect of exercise compliance. Importantly, these analyses will be hypothesis generating for future studies.

C3.8. Power calculation: The purpose of this clinical trial is to provide the preliminary data necessary to design a multicenter clinical intervention trial. Therefore, it is not strictly amenable to formal power

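### The 3-month surgery contrast cannot isolate weight-loss-independent effects by being early, because the protocol's own figures imply substantial weight loss by then

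*Protocol*

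**What the plan says.** Section C3.7.3 (Exploratory analyses) plans: "We will also investigate the potential weight loss independent effects of bariatric surgery by evaluating the earliest time point (3 months"). Section B (Innovation) lists the same idea in its sixth item, as an analysis of "the weight loss independent effects of bariatric surgery by incorporating early outcome measures". Neither place ties a weight-change term or a mediation model to the contrast. In the model of section C3.7.1 the covariates are demographic, clinical and baseline characteristics.

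The expected course of weight after surgery is in section C3.2.3: "weight loss is typically 60-80 pounds at 6 mo, and 100-120 pounds at one year with stabilization at 1-1.5 yr". No figure is given for 3 months, and nowhere is loss at 3 months said to be small.

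Table 6 (section C3.5) sets the visits at "Day -70 to 0 | Month 3 | Month 12 | Month 24", with a window of 14 days either side for the post-baseline visits. The event that defines Day 0 is not stated. BMI is measured at baseline and at 3, 12 and 24 months (section C3.3). Section C3.7.3 closes by calling its analyses hypothesis generating.

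**The concern.** The argument from timing needs a visit at which surgery has had its other effects but has not yet taken off much weight. If a large part of the weight is already gone by Month 3, a difference in IENFD between surgical and non-surgical patients at that visit may come from the weight loss, from something else about surgery, or from both. The contrast does not tell these apart.

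At stake is the interpretation of one exploratory result that the protocol advertises as an innovation. An early difference could be credited to a mechanism other than weight loss when the data do not support that attribution, and later work could be designed on that belief.

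**Working it through.** The protocol states no 3-month weight loss, so there is no figure to reproduce. The check interpolates from the values it does give.

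**Inputs**
- Loss W(6) = 60-80 lb and W(12) = 100-120 lb (C3.2.3); W(0) = 0 at surgery.
- Visit clock and window: Table 6.
- HIIT start in surgical patients: "Subjects receiving the surgery intervention will start the HIIT regimen no sooner than 4 wk post-operatively" (C3.2.1).
- Yardstick: the diet-induced weight-loss cohort, whose IENFD rose by only 0.2 fibers/mm "despite an average improvement in BMI of 3.67" kg/m² (C1.2.1).
- Cross-check: "Patients lose between 45-85% of their excess weight, with maximum weight loss between 1-2 yr after the procedure" (C2.2.1).
- Assumed, not in the protocol: height 1.67 m (range 1.55-1.85 m) and ideal BMI 25 kg/m².

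**Step 1: pace of loss.** Months 0-6: 60/6 = 10 to 80/6 = 13.3 lb per month. Months 6-12: (100 − 60)/6 = (120 − 80)/6 = 6.7 lb per month. Loss is fastest early.

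**Step 2: loss at 3 months, counted from surgery**

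| Curve | Formula for W(3) | Low | High |
|---|---|---|---|
| Linear, 0-6 months | W(6) × 3/6 | 30 lb | 40 lb |
| Quadratic through 0, 6, 12 months | 0.75·W(6) − 0.125·W(12) | 45 − 12.5 = 32.5 lb | 60 − 15 = 45 lb |
| Exponential to a plateau | A(1 − √r), r = W(12)/W(6) − 1, A = W(6)/(1 − r) | r = 0.667, A = 180: 33 lb | r = 0.5, A = 160: 47 lb |

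The linear figure is the lowest of the three because it ignores the slowing.

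**Step 3: share of the one-year loss**, low with low and high with high: 30/100 = 30% and 40/120 = 33%.

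**Step 4: sensitivity to the clock** (linear; month = 30.44 days, so 3 months = 91.3 days and 6 months = 182.6 days)

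| Month 3 counted from | Days since surgery | Loss |
|---|---|---|
| HIIT start, 28 days after surgery | 119.3 | 39-52 lb |
| Surgery | 91.3 | 30-40 lb |
| Baseline visit 28 days before surgery | 63.3 | 21-28 lb |
| Baseline visit 70 days before surgery | 21.3 | 7-9 lb |

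With the clock at surgery, the 14-day window (0.46 months) widens the range to 60 × 2.54/6 = 25 lb and 80 × 3.46/6 = 46 lb.

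**Step 5: comparison with the yardstick.** At 0.4536 kg per lb and 1.67 m, 30-40 lb is 4.9-6.5 kg/m²; across 1.55-1.85 m it is 4.0-7.6 kg/m². Both ranges lie above the 3.67 kg/m² of the diet cohort. The protocol treats that smaller loss as likely to matter for nerve outcomes: C1.2.1 expects some benefit from it, and C3.8 uses that cohort to set the expected change for surgery with routine counseling.

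**Step 6: cross-check on excess weight.** With the mean BMI of 45.7 in the bariatric cohort (Table 3), excess weight is (45.7 − 25) × 1.67²/0.4536 = 127 lb. Of this, 45-85% is 57-108 lb. Applying the shares from Step 3, 57 × 0.30 = 17 lb and 108 × 0.333 = 36 lb at 3 months. This is lower than Step 2 but not negligible.

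**The case against.** The strongest reply is that the text is cautious. It speaks of investigating potential effects, gives no labelling rule, and belongs to a paragraph declared hypothesis generating within a non-randomized, exploratory aim. A reader might infer that the plan would declare the whole 3-month difference independent of weight; the protocol does not say that. This stands, and it limits the point to what the named method can show.

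A second reply is that adjustment is provided for or belongs in an SAP. C3.3 allows phenotyping data to be used against confounding as needed, and the next sentence of C3.7.3 mentions analyses of other metabolic syndrome components. This stands only in part. Model detail may indeed be left to an SAP, but here the protocol names the means of separation, and it is timing. Weight lost after surgery lies on the causal path and is not a baseline confounder, and the neighbouring analysis is not linked to the 3-month contrast.

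A third reply is that 30-40 lb is not a protocol figure and depends on an undefined Day 0. That is correct. Only the extreme reading, a baseline visit 70 days before surgery, makes the loss small, and then only about three weeks of surgical exposure would have been observed.

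A reader might also infer that this analysis decides which mechanism to pursue. Sections A4 and C5 tie that choice to which intervention proves effective, so the inference has no support.

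**Conclusion.** The point holds in a limited form. Early timing alone cannot separate weight-loss-independent from weight-dependent effects of surgery, because substantial loss is expected by Month 3: roughly 30-40 lb, or 30-33% of the one-year loss. This assumes that Month 3 runs from surgery and that loss can be interpolated linearly. Slowing loss or a clock started at HIIT raises the figure; a clock started at an earlier baseline visit lowers it. Crossing opposite ends of the stated ranges (30/120 and 40/100) would give 25-40%, but that pairs the slowest early loss with the largest later loss and the reverse, so 30-33% is the fairer figure.

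The effect is on the interpretation of one exploratory analysis. A reader should not extend it to the primary analysis, which does not use this argument. Nor would adjusting for BMI change by itself turn the contrast into a weight-loss-independent effect: it conditions on a consequence of surgery in a comparison that is not randomized.

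**What to change.** In C3.7.3 and in item 6 of the innovation list, describe the 3-month comparison as an early effect of surgery and remove the claim of independence from weight loss. Define Day 0.

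Add a supplementary exploratory analysis along these lines: *The 3-month surgery contrast will be reported without and with adjustment for BMI change from baseline to 3 months (or by mediation analysis), after the distributions of BMI change in surgical and non-surgical patients have been compared. The adjusted result will not be interpreted as a direct effect of surgery if these overlap poorly.*

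State the assumptions beside it:
- no unmeasured confounding of surgery and IENFD, of surgery and weight change, or of weight change and IENFD;
- no confounder of weight change and IENFD that is itself affected by surgery (insulin sensitivity is a candidate);
- surgery-by-weight-change interaction examined.

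Overlap is a real worry. Section C3.8 expects about 30 patients per group after attrition, hence about 60 with and 60 without surgery. If non-surgical patients lose little weight by 3 months (an assumption), weight change will nearly duplicate the surgery indicator.

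The cost is a few sentences and one extra model on data already collected, with no new visit or measurement. The protocol gives up a stronger claim, and the adjusted contrast will have a wide interval.
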